8.1.3 Action

Eventual actions taken will be recorded.

8.1.4 Serious adverse events

A Serious Adverse Event (SAE) is defined by the International Conference on Harmonization (ICH) guidelines as any AE fulfilling at least one of the following criteria:

- results in death;
- is life threatening (at the time of the event);
- requires hospitalisation or prolongation of existing inpatients' hospitalisation;
- results in persistent or significant disability or incapacity;
- is a congenital anomaly or birth defect; or
- any other important medical event that did not result in any of the outcomes listed above due to medical or surgical intervention but could have been based upon appropriate judgement by the investigator.

An elective hospital admission will not be considered as a serious adverse event.

8.1.5 Reporting of serious adverse events

SAEs will be reported according to the following procedure.

The investigator will report the SAEs through the web portal ToetsingOnline (see https://toetsingonline.nl/) to the accredited EC that approved the protocol, within 7 days of first knowledge for SAEs that result in death or are life threatening followed by a period of maximum of 8 days to complete the initial preliminary report. All other SAEs will be reported within a period of maximum 15 days after the sponsor has first knowledge of the serious adverse events.

8.1.6 Follow-up of adverse events

All adverse events will be followed until they have abated or until a stable situation has been reached. Depending on the event, follow up may require additional tests or medical procedures as indicated, and/or referral to the general physician or a medical specialist.

8.2 Temporary halt for reasons of subject safety

In accordance to section 10, subsection 4, of the WMO, the investigator will inform the subjects and the EC if anything occurs, on the basis of which it appears that the disadvantages of participation may be significantly greater than was foreseen in the research proposal. The study will be suspended pending further review by the EC, except insofar as suspension would jeopardise the subjects' health. The investigator will ensure that all subjects are kept informed.

9 STATISTICAL METHODOLOGY AND ANALYSES

9.1 Statistical analysis plan

All safety and statistical programming is conducted with SAS 9.4 for Windows (SAS Institute Inc., Cary, NC, USA).

9.2 Protocol violations/deviations

Protocol deviations will be identified based on conditions related to the categories below:

- Protocol entry criteria
- Forbidden concomitant medications
- Missing evaluations for relevant endpoints
- Other protocol deviations occurring during study conduct.

Major protocol deviations will be identified before the study closure, and listed where appropriate.

9.3 Power calculation

This is an exploratory study and is therefore not based on statistical considerations.

9.4 Missing, unused and spurious data

All missing or incomplete clinical endpoints and data, including dates and times, are treated as such. Missing test results or assessments will not be imputed. Missing PD data, indicated as 'M' in the data listing, will be estimated within the statistical mixed model using SAS PROC MIXED.

For graphical and summary purposes PD and clinical endpoint values below the limit of quantification will be set to half (½) of the limit of quantification. For analysis no undetermined values will be replaced.

The handling of missing, unused and spurious data will be documented in the study report.

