1.1.4 Sample Size Justification

This is an exploratory study, therefore the samples size is not based on statistical considerations. The aim for this study is to enroll 200 subjects. The assays to determine $A\beta$ from CSF are well established methods and the sample size justification for this current study is therefore based on previous research on amyloid pathology in CSF. In this study we select elderly at the age of 65 and higher of which at least a hundred will be above the age of 70. According to Jansen et al., (2015) we can expect at least 19% amyloid pathology in a 65+ population and 23% amyloid pathology among cognitively healthy 70+ elderly subjects. As we expect more responsiveness for study participation from elderly between the age of 65 till 70, based on our experience with previous studies in this age range, at least 100 subjects of >70 years old will be included in this study to be able to differentiate between age, which results in approximately 23 A β positive subjects versus approximately 77 A β negative subjects in this elderly age group. Along with approximately 19 A β positive subjects versus approximately 81 A β negative subjects in the age group 65-70 we expect to find at least 42 A β positive healthy elderly subjects. Based on previous comparable studies, these numbers are considered appropriate for a correlational study aimed at defining an algorithm [22, 23].

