9.8 CNS and biochemical endpoints

9.8.1 NeuroCart

All parameters will be listed by subject.

Parameters will initially be analysed without transformation, but if the data suggest otherwise, log-transformation may be applied.

Descriptive statistics will be used to summarize the data. Data will be graphically processed for visual inspection.

In order to develop an algorithm that can classify the subjects between ADpath+ and ADpath- there will be a two-step procedure. In the first step 500 bootstrap samples will be generated out of the original data and logistic regression with LASSO penalization (in order to account for the expected small event per variable ratio) in each of the bootstrap samples with all the candidate variables (CNS and biochemical outcome variables, age and educational level) will be performed. Out of all the candidate variables the ones that consistently and most frequently appear in the bootstrap models will be selected. Hence, in this first step the variable selection will take place. In the second step another 500 bootstrap samples will be generated and logistic regression will be performed (with penalization if necessary) in each of the bootstrap samples. This time only the variables that were selected in step 1 will be entered in the model. The estimates out of all the bootstrap models will be averaged and used in order to obtain predictions in the original data. Step two will result in the bootstrap-corrected predictions that will be assessed in terms of calibration (calibration slope), discrimination (c-index) and squared mean prediction error.

To investigate the relationship between biomarkers and gene carriers and NeuroCart scores, correlations and regression analyses will be used.

NeuroCart scores will be analysed with an analysis of variance (ANOVA) and/or multivariate analysis of variance (MANCOVA) to estimate differences between the groups of elderly with different Aβ status.

The intra- and inter-individual diurnal fluctuation will be investigated with mixed-model analysis.

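### The no-imputation rule in section 9.4 leaves the step 1 LASSO model no way to keep a subject who lacks any one of about 62 candidate values

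*Protocol*

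**What the plan says.** Protocol section 9.4 sets three rules that matter here.

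- For gaps in general: "Missing test results or assessments will not be imputed".
- For missing PD data: they "will be estimated within the statistical mixed model using SAS PROC MIXED".
- For values below the limit of quantification: PD and clinical endpoint values are set to half the limit for graphs and summaries, but "For analysis no undetermined values will be replaced".

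Section 9.8.1 describes the algorithm that serves the main objective. Step 1 draws 500 bootstrap samples and fits a LASSO logistic regression in each; the text reads "with all the candidate variables (CNS and biochemical outcome variables, age and educational level) will be performed". Step 2 draws another 500 samples and enters only the variables selected in step 1.

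Section 9.5 admits data from all participants where they can usefully serve the objectives. Section 9.4 adds that the handling of missing data will be described in the study report. Neither names a method for an incomplete record in the logistic model.

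**The concern.** A penalised logistic regression is fitted to a complete matrix of predictors. If a blank may be neither imputed nor replaced, a subject with one blank cannot enter step 1, however complete the rest of the record.

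The mixed-model sentence does not help. A mixed model accommodates missing responses in a repeated series, which suits the diurnal plasma analysis. It does not fill in predictors for a different model, and Table 1 schedules each NeuroCart test once on the study day, so there is no repeated series to borrow from.

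One gap is built in. Section 7.3 derives the SART post-error slowing score from commission errors alone, and section 6.2 lists that score as an endpoint, so it is a candidate. A subject with no commission error has no score. Under section 9.4 the best performers on that test would leave variable selection even if data collection were perfect.

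At stake are the roughly 42 expected Aβ-positive subjects, the limiting resource for the algorithm, and a selection step that favours subjects with every score present.

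**Working it through.** **The plan's own figure.** Section 1.1.4: "The aim for this study is to enroll 200 subjects", with at least "19% amyloid pathology in a 65+ population and 23% amyloid pathology among cognitively healthy 70+ elderly subjects". Applied to 100 subjects in each age group: 100 × 0.23 + 100 × 0.19 = 23 + 19 = 42. This reproduces the statement that "we expect to find at least 42" positives.

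**Number of candidates**, counted from sections 6.2 and 6.3, taking one value per plasma marker and leaving out the CSF and exploratory markers:

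- Tracking 1, VVLT 6, Milner Maze 9, faces 2, N-back 6, SART 6, tapping 2, EEG 15, saccades 3, smooth pursuit 1, CDR 1, IADL 1, grip 1: total 54.
- Plasma markers 5, APOE 1, age 1, education 1: total 8.
- 54 + 8 = 62.

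The count is 64 with the screening-only GDS-15 and MMSE, 61 without plasma p-Tau (section 7.2.3 describes p-Tau for CSF only), and 60 without CDR and IADL.

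**Number of blocks**, if a whole test or sample is missing at once: tracking, VVLT, maze, faces, N-back, SART, tapping, EEG, eye movements, CDR, IADL, grip, plasma panel, APOE. That is 14, or 15 if saccades and smooth pursuit are separate. Age and education are taken as complete.

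**Complete-case share** = (1 − m)^k, where m is the share missing per unit and k the number of units. The protocol gives no m; 0.5% and 1% are assumptions. Loss is taken to be equal in positives and negatives.

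| Unit | k | m | Share kept | Loss | Subjects of 200 | Positives of 42 |
|---|---|---|---|---|---|---|
| Test | 14 | 0.5% | 0.932 | 6.8% | 186 | 39.2 |
| Test | 15 | 0.5% | 0.928 | 7.2% | 186 | 39.0 |
| Test | 14 | 1% | 0.869 | 13.1% | 174 | 36.5 |
| Test | 15 | 1% | 0.860 | 14.0% | 172 | 36.1 |
| Variable | 62 | 0.5% | 0.733 | 26.7% | 147 | 30.8 |
| Variable | 62 | 1% | 0.536 | 46.4% | 107 | 22.5 |

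**Events per candidate.** With nobody lost: 42/62 = 0.68. By variable: 30.8/62 = 0.50 at 0.5% and 22.5/62 = 0.36 at 1%.

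**Rate needed to lose a quarter or a half**, m = 1 − (1 − loss)^(1/k). By variable (k = 62): 0.46% and 1.11%. By test (k = 14 to 15): about 1.9% to 2.0%, and about 4.5% to 4.8%.

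**One further source of gaps.** If a share s of subjects lacks one more value (no SART commission error, or one plasma marker below quantification and treated as missing), the loss is 1 − (1 − s)(1 − m)^k. With m = 1% and k = 14:

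- s = 5%: 1 − 0.95 × 0.869 = 17.5%
- s = 10%: 1 − 0.90 × 0.869 = 21.8%

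The protocol gives no value for s in either case; these are illustrations.

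**The case against.** A reader might infer that the plan will lose a quarter to half of the cohort. The documents do not support that. It needs about 0.5% to 1.1% missing independently in each of 62 variables, and the variables are not independent: 15 EEG values come from one recording, nine maze scores from one test, and SART total errors is the sum of two other listed scores. By whole test, the same loss needs about 2% to 5% per test, for which the protocol gives no basis. The design also limits gaps: one supervised visit of about four hours, a training session that screens for ability to do the tests, and possible replacement of withdrawals. This objection stands, and the by-test figures are the more natural reading.

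Listwise deletion is inferred rather than stated, and full deletion over all candidates applies only to step 1. Both points are right. Neither removes the gap, because the rules leave no other stated way to fit step 1, and step 1 fixes which variables the algorithm contains.

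A reader might also infer that the lowest biomarker values are certain to be discarded. That is not established. The half-limit sentence names PD and clinical endpoints, whereas section 6.3 lists the markers as biochemical endpoints. The term for values that are not replaced is left undefined. No limit or expected share below it is given, and the assay is described as ultrasensitive.

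Nor does section 9.4 misclassify a CSF Aβ 1-42 result below quantification. If the limit lies under 450 pg/mL, such a result already meets the ADpath+ definition in section 4.4 and needs no number.

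Details of imputation are commonly left to the SAP. Here, however, the protocol states a prohibition, and an SAP that imputed would contradict it.

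**Conclusion.** The point holds as a mismatch between a stated rule and the main model. Section 9.4 bars imputation, its mixed-model provision does not reach the predictors of the step 1 LASSO regression, and a subject with one missing candidate therefore drops out of variable selection. Subjects with no SART commission error would drop out for that reason alone.

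The size depends on a rate that the protocol does not give. At an assumed 0.5% to 1% missing, step 1 loses about 7% to 14% of subjects if gaps occur by whole test and 27% to 46% if they are independent by variable. Step 2 loses less, since it needs only the selected variables. These figures take losses to be equal in positives and negatives and exclude the SART and below-quantification gaps, which would add to them.

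The below-quantification harm is conditional: if such plasma values occur, and if they are treated as missing, the loss is informative because the values are known to be low. The study is exploratory and tests no formal hypothesis, but the rule bears directly on its main objective.

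**What to change.** For the algorithm only, amend section 9.4 as follows.

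1. Replace the no-imputation rule with multiple imputation of missing candidate predictors inside each bootstrap resample. Put ADpath status in the imputation model, because omitting the outcome would weaken the associations the model is meant to find. Leave the other CSF markers out. Keep every subject with a CSF Aβ 1-42 result.
2. Drop SART post-error slowing from the candidate pool, or code it so that error-free subjects are retained.
3. Use one below-quantification rule for plasma markers in both summaries and analysis, either half the limit or a censored-value method, and say explicitly that it covers the biochemical endpoints.
4. State that a CSF Aβ 1-42 result below a limit that lies under 450 pg/mL counts as ADpath+ under the existing definition.
5. Report the complete-case analysis as a sensitivity analysis.
6. Limit the PROC MIXED sentence to the diurnal model.

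With this change all subjects with an outcome stay in step 1: up to 200 subjects and about 42 positives, or 0.68 events per candidate. The cost is a few sentences and some extra programming, with no change to visits or samples. The statistical price is a missing-at-random assumption, which the complete-case analysis helps to examine.

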9.5 Analysis sets

Data of all subjects participating in the study will be included in the analyses if the data can meaningfully contribute to the objectives of the study.

9.6 Subject disposition

Subject disposition will be listed by subject.

The following subject data will be summarized:

- Number and percentage of subjects screened,
- Number and percentage of subjects enrolled,
- Number and percentage of subjects included in the PD analysis population.
- Number and percentage of subjects completed,

A subject who completed the study is defined as a subject where the 4 hour biomarker plasma sample was assessed.

9.7 Baseline parameters and concomitant medications

9.7.1 Demographics and baseline variables

Continuous demographic variables (e.g., age, height, weight, BMI) will be summarized by descriptive statistics (n, mean, SD, median, Min, Max).

Qualitative demographic characteristics (sex, race/ethnicity) will be summarized by counts and percentages.

9.7.2 Medical history

Medical history will only be listed.

9.7.3 Concomitant Medications

All concomitant medications will be displayed in a listing.

9.7.4 Adverse events

The AE coding dictionary for this study will be Medical Dictionary for Regulatory Activities (MedDRA). It will be used to summarize both the number of events and the number of subjects with an AEs by primary system organ class (SOC) and preferred term (PT). All adverse events will be displayed in listings.

9.8 CNS and biochemical endpoints

9.8.1 NeuroCart

All parameters will be listed by subject.

Parameters will initially be analysed without transformation, but if the data suggest otherwise, log-transformation may be applied.

Descriptive statistics will be used to summarize the data. Data will be graphically processed for visual inspection.

In order to develop an algorithm that can classify the subjects between ADpath+ and ADpath- there will be a two-step procedure. In the first step 500 bootstrap samples will be generated out of the original data and logistic regression with LASSO penalization (in order to account for the expected small event per variable ratio) in each of the bootstrap samples with all the candidate variables (CNS and biochemical outcome variables, age and educational level) will be performed. Out of all the candidate variables the ones that consistently and most frequently appear in the bootstrap models will be selected. Hence, in this first step the variable selection will take place. In the second step another 500 bootstrap samples will be generated and logistic regression will be performed (with penalization if necessary) in each of the bootstrap samples. This time only the variables that were selected in step 1 will be entered in the model. The estimates out of all the bootstrap models will be averaged and used in order to obtain predictions in the original data. Step two will result in the bootstrap-corrected predictions that will be assessed in terms of calibration (calibration slope), discrimination (c-index) and squared mean prediction error.

To investigate the relationship between biomarkers and gene carriers and NeuroCart scores, correlations and regression analyses will be used.

NeuroCart scores will be analysed with an analysis of variance (ANOVA) and/or multivariate analysis of variance (MANCOVA) to estimate differences between the groups of elderly with different Aβ status.

The intra- and inter-individual diurnal fluctuation will be investigated with mixed-model analysis.

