A recent study by Lutz et al., (2016) describes a genetic-based biomarker algorithm for risk of AD development. The authors used genetic and biomarker (CSF) data from cognitively normally, MCI and AD subjects who were followed longitudinally. They included age, APOE and TOMM400'523 genotypes [18]. This study, however, was aimed at predicting conversion to clinically over dementia in subjects at risk for AD, while we intend to develop an algorithm that aims at identifying subjects at risk of having a biomarker profile consistent with AD among healthy elderly subjects. A number of variables will serve as a pre-selected pool of candidate variables and will be used in this study to develop the algorithm; plasma-based biomarkers (i.e. $A\beta40$, $A\beta42$, t-Tau, p-Tau and Neurofilament Light [NfL]), apolipoprotein ϵ (APOE ϵ) genotyping, age, educational level, grip strength and neuropsychological and neurophysiological testing by means of a computerized test battery (i.e. NeuroCart) (for further details, see methods).

Subjects will be asked to undergo a LP to quantify AD-specific biomarkers in CSF. Based on comparable studies, the expectation is that approximately 20% of subjects who are approached will be willing to undergo a LP. In this study we aim to enroll a study population of 200 subjects and therefore think we will need to approach approximately 1000 subjects.

Plasma levels of Aβ40, Aβ42 and NfL, APOE ϵ status and NeuroCart tests of the 200 subjects will be used to define an algorithm that will be able to improve the efficiency of finding subjects who have an Aβ positive (CSF) profile. The subjects will be divided in a group yielding subjects who are suspected of AD pathology (ADpath+) by the algorithm and subjects who are suspected to be without AD pathology (ADpath+). To confirm the correct classification potential of the algorithm, the outcome will be compared to the CSF Aβ outcome of the subjects. CSF ADpath+ and a CSF ADpath- defined by an Aβ 1-42 CSF level ≤450 pg/mL for ADpath+ subjects and an Aβ 1-42 CSF level ≥451 pg/mL for ADpath- subjects, will be used to differentiate between the two groups (using the Single Molecule Array assay; Simoa assay [19]).

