1.1 Study rationale

1.1.1 Benefit and risk assessment

This is a study without an intervention (e.g. novel drug administration) which makes the risk of injuries or side effect from drug administration none. Taking blood samples can be an unpleasant procedure and can lead to bruises. The CSF sampling could be an uncomfortable procedure and may lead to side effects, for instance post-dural puncture headache or bruising.

There is no benefit for the subjects who participate in the study. This study increases the knowledge about possible relationships between different types of blood plasma biomarkers in this specific cohort of elderly. The study may yield an algorithm (base on e.g. the NeuroCart results, CSF information and plasma based biomarkers from the subjects) that can be used to predict the likelihood that an otherwise healthy subject has AD pathology before clinical disease onset. This may lead to fewer lumbar punctures in future studies aimed at finding subjects to participate in clinical trials with drugs aiming at slowing AD disease onset. Subjects of this current study may be asked to participate in future studies.

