1.1.8 Biochemical outcome variables

CSF biomarkers

- Aβ concentration (1-40, 1-42 and 1-42/1-40 ratio);
- T-Tau and p-Tau concentrations;
- NfL concentration.

Plasma biomarkers

- Aβ concentration (1-40, 1-42);
- T-Tau and p-Tau concentrations;
- NfL concentration.

Exploratory biomarkers including but not limited to:

- Synaptic loss; Neurogranin [24],
- Glial inflammation; YKL-40 [25],
- Levels of p-Tau181 in extracts of neutrally-derives blood exosomes [26],
- MicroRNAs [MiR-155, MiR-107 and MiR-29 [27]]).

Genetics

APOE ε genotype;

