2 STUDY OBJECTIVES

Main objectives:

To define an algorithm based on the plasma biomarkers: A β 40, A β 42, t-Tau, p-Tau, NfL and APOE ϵ status and NeuroCart tests, age, grip strength and level of education that distinguishes between positive and negative A β CSF in healthy elderly.

Exploratory objective:

To determine the correlation between AD-specific biomarkers in CSF (Aβ 1-40 and 1-42, Tau proteins, NfL) and the NeuroCart scores in a cohort of 200 healthy elderly subjects.

To determine the correlation between AD-specific biomarkers in plasma (Aβ 1-40 and 1-42, Tau proteins, NfL) the NeuroCart scores in a cohort of 200 healthy elderly subjects.

To determine the correlation between AD-specific biomarkers in CSF (Aβ 1-40 and 1-42, Tau proteins, NfL) and in plasma in a cohort of 200 healthy elderly subjects.

To determine the correlation between APOE ϵ genotype and the A β /Tau/NfL concentrations in CSF in a cohort of 200 healthy elderly subjects.

To determine the correlation between APOE ϵ genotype and the A β /Tau/NfL concentrations in plasma in a cohort of 200 healthy elderly subjects.

To characterize the cohort of healthy elderly subjects in order to yield norm scores for specific NeuroCart tests in all subjects.

To characterize the plasma biomarkers across multiple times of day to gain understanding of intraand inter-subject variability, and thus diurnal fluctuation.

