4.4 Study population subgroups

General cognitive functioning, dementia status and depressive status will be assessed at pre-study screening. All subjects eligible according to the in- and exclusion criteria will be entered in the study. Subjects will be asked to give consent for a LP.

Plasma levels of A β 40, A β 42 and NfL, APOE ϵ status and NeuroCart tests of the 200 subjects will be used to define an algorithm that will be able to improve the efficiency of finding healthy subjects who have an A β positive (CSF) profile. The subjects will be divided in a group yielding subjects who are suspected of AD pathology (ADpath+) by the algorithm and subjects who are suspected to be without AD pathology (ADpath-)

To confirm the correct classification potential of the algorithm, the outcome will be compared to the CSF Aβ outcome of the subjects. CSF ADpath+ and a CSF ADpath- defined by an Aβ 1-42 CSF

level ≤450 pg/mL for ADpath+ subjects and an Aβ 1-42 CSF level ≥451 pg/mL for ADpath- subjects, will be used to differentiate between the two groups.

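### The candidate set written into the algorithm analysis (9.8.1) admits the CSF biomarkers, including the CSF Aβ 1-42 value that defines ADpath status, and so contradicts the CSF-free candidate pool and main objective

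*Protocol*

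**What the plan says.** **The analysis rule.** Section 9.8.1 develops the algorithm in two bootstrap steps. Step 1 fits LASSO logistic regression "with all the candidate variables (CNS and biochemical outcome variables, age and educational level) will be performed". The same sentence stands in 1.1.9 and in the synopsis under statistical methodology. None of the three restricts the biochemical variables to plasma or excludes CSF.

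**What the term covers.** Section 1.1.8 is headed Biochemical outcome variables. Its first list, under CSF biomarkers, opens with "Aβ concentration (1-40, 1-42 and 1-42/1-40 ratio") and goes on to CSF t-Tau, p-Tau and NfL. Plasma markers, an exploratory list that is expressly not closed, and APOE genotype follow. Section 6.3 repeats the content.

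**The outcome.** Section 4.4 defines the classes by an Aβ 1-42 CSF "level ≤450 pg/mL for ADpath+ subjects and an Aβ 1-42 CSF level ≥451 pg/mL for ADpath- subjects". Section 1 and the synopsis give the same definition.

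**The intended predictors.** The main objective in section 2 is "To define an algorithm based on the plasma biomarkers" Aβ40, Aβ42, t-Tau, p-Tau and NfL, together with APOE status, NeuroCart tests, age, grip strength and education. Section 1 says "A number of variables will serve as a pre-selected pool of candidate variables" and names the same items. Neither includes a CSF measurement.

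**Two further statements.** Sections 1 and 4.4 and the synopsis background also give a shorter list: plasma Aβ40, Aβ42 and NfL, APOE and NeuroCart. Section 1.1.1 describes the algorithm as "base on e.g. the NeuroCart results, CSF information and plasma based biomarkers from the subjects".

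**The concern.** The sentence that a programmer would implement points to a heading whose contents include the outcome variable. A model that may use CSF Aβ 1-42 to predict a threshold on CSF Aβ 1-42 says nothing about blood, genotype or cognitive tests.

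That particular error would be noticed, because discrimination would be perfect. The less visible risk lies with the other CSF measures. The Aβ 1-42/1-40 ratio has the outcome variable as its numerator, and CSF Aβ 1-40, tau or NfL could be selected without any obvious sign of trouble. A model that keeps any of them cannot be used to decide who may be spared a lumbar puncture, which is the purpose given in section 1.

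A third consequence is freedom of choice. With differing descriptions of the candidates in one protocol, the set can be settled after the data have been seen. About 42 positive subjects are expected, and the protocol itself anticipates few events per variable.

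**Working it through.** **1. Does the bracket point to the headings?** CNS outcome variables and Biochemical outcome variables are the titles of 1.1.7 and 1.1.8. Grip strength is listed under the first and APOE under the second, and the bracket names neither separately. Age and education are under neither heading, and the bracket adds them by name. The bracket thus reproduces the intended pool only if it refers to those two headings. The reading that brings in APOE also brings in the CSF list.

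**2. What the literal rule adds.**

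| Item | 9.8.1, 1.1.9, synopsis methodology (literal) | Section 2; pool in section 1 | Short list in sections 1 and 4.4 |
|---|---|---|---|
| Plasma Aβ40, Aβ42, NfL | yes | yes | yes |
| Plasma t-Tau, p-Tau | yes | yes | no |
| APOE, NeuroCart | yes | yes | yes |
| Age, education, grip strength | yes | yes | no |
| CSF Aβ 1-40, Aβ 1-42, ratio, t-Tau, p-Tau, NfL | **yes (6)** | no | no |
| Exploratory biomarkers (open list) | **yes** | no | no |
| CDR, IADL | **yes** | not named | not named |

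**3. The protocol's own event count.** Section 1.1.4 expects 100 × 0.23 + 100 × 0.19 = 23 + 19 = 42 positives, hence 200 − 42 = 158 negatives. The stated figure of 42 reproduces.

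**4. c-index if CSF Aβ 1-42 is a predictor.** The c-index is the share of positive–negative pairs in which the positive subject has the higher predicted risk. Take risk as decreasing in CSF Aβ 1-42. Every positive has a value of at most 450 and every negative a value of at least 451, so every pair is concordant. With the expected numbers there are 42 × 158 = 6,636 pairs, and 6,636/6,636 = 1.00. The result follows from the definition and holds for any number of positives.

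**5. Would LASSO select it?** An illustrative simulation used n = 200, 21% positive, the outcome as a threshold on one normal variable, and 64 independent noise variables beside it. The 64 is a simulation setting, and no conclusion here rests on it. Penalties were fixed at 0.04 (selection) and 0.01 (re-estimation), five variables were kept, and there were 50 bootstraps per step (the protocol has 500) and 15 replicates. The defining variable was selected in 100% of bootstraps. The c-index was 1.00 in the original data and 1.00 in new data.

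**The case against.** The strongest reply is that the protocol defines its candidates elsewhere. Section 1 introduces "A number of variables will serve as a pre-selected pool of candidate variables" and lists it without any CSF item, section 9.8.1 uses the same term, and its bracket could be taken as loose shorthand for that pool. The main objective agrees. CSF Aβ is treated as the reference: "To confirm the correct classification potential of the algorithm, the outcome will be compared to the CSF Aβ outcome of the subjects".

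This stands as far as intent goes. A reader might infer from 9.8.1 that the plan as a whole uses the outcome to predict itself, and the documents do not support that. The objective, the pool and the rationale all run against it. The reply does not remove the defect, because the rule is stated three times in terms that include CSF, and steps 1 and 2 of the working show that this is the natural reading of the bracket.

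Three further limits should be accepted:

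- The mention of CSF information in 1.1.1 is an example given in passing in a benefit–risk paragraph. CSF is needed in development to supply the class label, so the phrase has an innocent reading and is weak evidence on its own.
- The short list in sections 1 and 4.4 may be an abbreviation. Section 1 carries both lists.
- A reader might also infer that the logistic coefficients must diverge. Complete separation does that only in an unpenalised fit. Step 1 is penalised and step 2 allows penalisation, so finite estimates are possible.

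**Conclusion.** The point holds as a contradiction between the stated analysis rule and the stated objective. As written, the candidate set in 9.8.1, 1.1.9 and the synopsis admits six CSF measures, one of which defines the outcome, and an open exploratory list. The main objective and the pool in section 1 admit none of these. The rule itself is wrong as stated, so this is more than detail left to a statistical analysis plan.

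The consequence depends on literal implementation. In that case CSF Aβ 1-42 gives a c-index of exactly 1.00, and this needs no assumption beyond the class definition. The 100% selection frequency is illustrative and rests on the simulation settings given. That any other retained CSF analyte defeats the purpose follows from the rationale alone. The documents do not show that anyone plans to enter CSF variables.

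**What to change.** In 9.8.1, 1.1.9 and the synopsis methodology, replace the bracket with the closed list already given in sections 1 and 2: plasma Aβ40, Aβ42, t-Tau, p-Tau and NfL; APOE ε genotype; NeuroCart tests; age; grip strength; educational level. Add that no CSF analyte is a candidate predictor and that CSF Aβ 1-42 serves only as the outcome.

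In 1.1.1, make clear that CSF supplies the class label only. Align the shorter lists in section 1, section 4.4 and the synopsis background with section 2.

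Two loose ends should be settled in the same edit. CDR and IADL fall under the CNS heading but are not named in section 2, so the closed list leaves them out unless the sponsor adds them explicitly. Section 7.2.3 describes the p-Tau assay for CSF only, so the plasma p-Tau entry needs confirming.

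The cost is protocol wording, carried into the statistical analysis plan. No change to data collection or sample size follows.
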